To assess the effectiveness of this multilevel intervention, called the workplace *Metabolic Health Improvement Program (MHIP)*, we will conduct a double-randomized trial in partnership with the clinical trials division of a large Northern California-based academic healthcare system, Sutter Health ($N=700$ employees on $N=16$ hospital campuses). We will first cluster-randomize 8 Sutter Health hospital campuses to the SSB sales ban condition and 8 campuses to serve as controls (no sales ban). Across these 16 campuses, we will further randomize heavy-SSB-consuming employees (>30 oz/week) to receive a brief SSB counseling intervention delivered remotely or to a control condition.^{11,12} The **primary outcomes** are central obesity (e.g., waist circumference) and change in serum insulin sensitivity (homeostatic model assessment [HOMA] ratio). **Secondary outcomes** include changes in SSB consumption, Body Mass Index (BMI), and lab values to include: lipid profile, triglycerides, triglyceride:HDL ratio, uric acid, ApoA, ApoB, lactate, ALT/AST, GGT, fasting glucose, fasting insulin, HbA1c. We will assess dietary composition remotely using the Automated Self-Administered 24-hour (ASA-24) at baseline, 6 and 12 months, and waist circumference remotely with empirically validated instructions and a standardized tape measure provided to participants. We will collect blood samples in the workplace labs at baseline and 12 months. All analyses will consider compensatory changes in at-home SSB intake, calories from sugar, and total calories. Aims are:

Aim 1: How well does each intervention work alone? We will assess the independent effects of the brief counseling intervention and workplace SSB sales ban on changes in primary and secondary outcomes. We will compare outcomes across employees exposed to the brief intervention only ($n=175$), SSB sales ban only ($n=175$), and no intervention ($n=175$). *We hypothesize that the brief counseling intervention and sales ban will each independently decrease waist circumference and HOMA relative to no intervention. Those at high risk (baseline BMI >25 , ethnic-minority, and lower-occupational status) will benefit more from the interventions.*

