Public health impact: If effective, the proposed employer-sponsored multilevel intervention will offer an efficient, scalable strategy for preventing obesity in millions of American working adults. This study will also contribute to science on mechanisms of change in obesity prevention and inform the design of interventions that exploit synergies between individual behavior change strategies and food environment policies.

4. METHODS:

(4a) General Study Design:

This is a prospective, double-randomized study in which 16-Sutter Health affiliate hospital campuses will be cluster randomized to control (no SSB sales ban) vs. intervention (removal of SSBs). Across these 16 campuses, we will enroll 700 employees and then randomize those who self-report consuming >30 oz of SSB per week to receive a brief counseling intervention or control (no intervention).

**SUTTER HEALTH
INSTITUTIONAL REVIEW BOARD**

Protocol Summary Form

(4b) Procedures:

Cluster Randomization of 16 Sutter Health Affiliates

Sutter Health affiliates will be eligible to participate in the study who meet the criteria: 1) the affiliate has not participated in a SSB intervention; 2) the affiliate is not in a county that has instituted a SSB sales tax. Affiliates will be stratified by their location (urban vs. rural) and number of employees and will be randomly assigned using a computer program to be assigned to either control or intervention. Sutter Health leadership ([name] and [name]) have signed a letter of support to conduct this study.

Sites randomized to the SSB will eliminate sugar-sweetened beverages from the cafeterias, vending machines, Walgreens, vendors, and from patient care areas. Sutter Health has already implemented Healthy Beverage Initiatives (HBI) at Alta Bates, Palo Alto Medical Foundation (PAMF) and all CPMC campuses.

Study Procedure	Description	Baseline	6 Months	12 Months
Informed Consent	Procedures Described Below	X		
Demographics	Self-reported gender, ethnicity, household income, education, work location, hours, shifts	X	X	X
Medical History	Self-reported concurrent medications and general medical history with an emphasis on diabetes	X	X	X
Height	Measured using a stadiometer on a standardized scale at a semi-private location on the affiliate campus.	X		
Weight	Obtained on a standardized scale at a semi-private location on the affiliate campus.	X	X	X

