Waist Circumference	A tape measure with instructions will be provided to the participant to measure at the designated timepoints.	X	X	X
Fasting Blood Draw	The collection will include: complete metabolic and lipid panel, uric acid, ApoB, GGT, glucose, insulin, HbA1c. These are biomarkers that are risk factors for poor metabolic health, diabetes, and cardiovascular disease	X		X
BevQ	This questionnaire seeks to quantify the frequency, type and volume of beverages consumed at work and home.	X	X	X

**SUTTER HEALTH
INSTITUTIONAL REVIEW BOARD**

Protocol Summary Form

ASA 24	This is a web-based, 24-hour dietary recall tool developed by the National Cancer Institute	X	X	X
Stanford Leisure Time Scale (L-CAT)	This is a scale that measures physical activity.	X	X	X
*PROMIS4a Depression	Assesses the presence and severity of symptoms of depression.	X	X	X
Beverage Craving Questionnaire (FCQ-T-R)	Assesses the following: 1) preoccupation with sweetened beverages; 2) loss of control; 3) positive outcome expectancy; 4) emotional cravings	X		
Reward Based Eating Drive (RED-13)	Assesses three aspects of drive to eat: 1) loss of control; 2) lack of satiety; 3) preoccupation with food	X	X	X
Perceived Stress Scale	This is a widely used questionnaire to assess stress levels. It evaluates the degree to which an individual has perceived life as unpredictable, uncontrollable, and overloading over the previous month.	X	X	X
Copenhagen Burnout Inventory (CBI)	This six-item inventory measures personal burnout experienced by participants.	x	x	x
Self-Efficacy	These questions are used to determine if an individual exhibits intention to reduce SSB consumption.	X	X	X
Science of Behavior Change Texts Parent Grant	Assesses craving, psychological stress, consumption and self-efficacy (two texts/day x four days/week)	X	X	X
Science of Behavior Change Texts Supplemental Grant	Assesses craving, psychological stress, consumption and self-efficacy (two texts/day x four days/week)	Additional texts will be sent at the following time periods: 1, 2, and 3 months after SSB intervention.		
EPIC EMR	Lab results from the blood draw will be extracted from EPIC utilizing the resources of the Center for Health Services Research (CHSR). Limited data from the medical record will be extracted by CHSR that looks at metabolic health.	X		X
Incentive Gift		X	X	X

**SUTTER HEALTH
INSTITUTIONAL REVIEW BOARD**

Protocol Summary Form

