***Patient-Reported Outcomes Measurement Information System (PROMIS):** We have selected a self-report measures of depression which are person-centered which all study participants will be asked to complete. We will investigate the possible correlation between SSB consumption, general health and depression as well as change over time between the intervention and control campuses. Subjects who report high levels of depression will be provided with contact information to Sutter Health's Employee Assistance Program (EAP). No documentation will be placed in the subject's medical or employment record.

REDCap will be set-up with a notification alerting the CRCs when the depression scores result with severe depression. When the participant completes their questionnaires, the Clinical Research Coordinators will review the depression questionnaire. If a participant scores a severe depression (score, a phone call will be made to the participant using a script. A form has been created and will be used as documentation. This includes a script for leaving a message and for a live call. During a live call only, the Clinical Research Coordinator will inform the participant of their high score and will with the phone number to Sutter Health's EAP.

Demographics: Including gender, ethnicity, primary work location, occupational status, income, and usual number of worked shifts each week will be recorded via REDCap.

Medical History: Concurrent medications and general medical history will be obtained directly from study participants with an emphasis on metabolic history such as diabetes. Data will be recorded via REDCap

Height, weight, and waist circumference measurements: Subjects will be asked to record their self-reported height in REDCap. Height and weight will be measured using a standard scale with an attached stadiometer in a semi-private location at the affiliate and record their weight and height in REDCap. A tape measure and instructions on measuring waist will be sent to the participant's home. They will record the measurement in REDCap.

Fasting Blood Draw: A fasting blood draw will take place at the draw station of the local affiliate. Labs will be drawn at baseline and at 12-months. The panels will be comprised of metabolic and lipid panels that pertain to metabolic syndrome. Labs will be accessible to participants using My Health Online.

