Power Calculations: Power calculations are based on changes observed in the pilot study and response rates from the current Sutter Health trial. Calculations are conservative, based on 80% retention of participants after 12 months. With an initial N of 700 drawn from 16 Sutter Health sites randomly assigned to the sales ban and control conditions, and with participants within those sites randomly assigned to brief intervention/no brief intervention conditions, 80% retention would result in an overall N of 550 at 12 months. This results in approximately 138 in each of four experimental conditions: brief intervention + sales ban, the brief intervention only, sales ban only, and no intervention. Power analysis for a full factorial design conducted with the BDEsize¹⁰⁹ package within R¹¹⁰ indicates that with 80% power and an alpha level of .05, we will be able to detect effect sizes as small as .08 for the effect of each intervention on each outcome.

Anticipated Problems and Alternative Approaches: One potential problem is attrition, particularly biased attrition. We have calculated the sample to allow for up to 20% attrition; this is a conservative number based on our current Sutter Health data. In the UCSF pilot, which took place entirely pre-pandemic, we achieved a 94.4% response rate for blood draws. The existing study team has experience with the challenges of retaining a sample of health care workers during a challenging time and can use the same techniques (e.g., email and phone outreach) to reduce attrition here. We will conduct statistical tests to determine if attrition is biased on baseline risk levels, demographic factors (including regional differences), or study condition.

As with all self-report data, the survey data on SSB consumption could be biased, perhaps particularly for intervention participants who want to self-present improvement. However, the anthropometric and blood measures are objective and should show a consistent pattern with the SSB changes. Standard data cleaning procedures should reveal any extreme cases of self-representation bias. For SSB consumption data, we have also established a convention in previous studies of pruning outliers that are more than 4 SD away from the mean to reduce error from participants who may have responded inaccurately.

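### Self-measured waist, a primary outcome, cannot serve as an objective check on self-report bias; only the laboratory measures can

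*Combined protocol and SAP*

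**What the plan says.** Section 1 (Study Aim/Purpose) states that the primary outcomes "are central obesity (e.g., waist circumference) and change in serum insulin sensitivity (homeostatic model assessment [HOMA] ratio"). It says that staff will assess "waist circumference remotely with empirically validated instructions and a standardized tape measure provided to participants". The procedures table in section 4b repeats this for baseline, 6 and 12 months: "A tape measure with instructions will be provided to the participant to measure at the designated timepoints". The text under the table adds: "A tape measure and instructions on measuring waist will be sent to the participant's home. They will record the measurement in REDCap". No staff reading or verification of waist is described.

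The same paragraph of 4b has height and weight taken on a campus scale with a stadiometer, but participants record these values too. Blood is drawn at the affiliate's draw station, at baseline and 12 months only.

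Section 4c, Aim 1, Anticipated Problems and Alternative Approaches, concedes that "the survey data on SSB consumption could be biased, perhaps particularly for intervention participants who want to self-present improvement". Its main answer is: "However, the anthropometric and blood measures are objective and should show a consistent pattern with the SSB changes". The paragraph on multiple outcomes at the end of that subsection then relies on whether each result fits the overall pattern, and it counts the anthropometric measurements among the related measures that make up the pattern. Aim 2 refers back to the same handling.

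**The concern.** The plan anticipates a bias that differs by arm, which randomization does not remove. It proposes to detect it by comparison with measures said to be objective. Waist is taken and entered by the same people whose reports are in doubt, so it can carry the same wish to show improvement.

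Two things are at stake. First, a small arm-dependent shading of the tape reading would appear as an adiposity effect on a primary outcome. Second, reported intake and waist could agree because both are biased in the same direction, and the plan as written would read that agreement as reassurance.

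**Working it through.** **Comparing the sections**

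1. *Who produces the waist value?* The participant, remotely, at all three time points (section 1; section 4b, table and text).
2. *Can participants tell their exposure?* The documents do not mention blinding, so this is inferred from the design. Employees are randomized "to receive a brief counseling intervention or control (no intervention"), with no sham contact. The coached group receives a session and two booster calls. Ban campuses remove the drinks from cafeterias and vending machines. Neither exposure can be hidden.
3. *Which readings are exposed?* Baseline waist is one of the five measurements completed before counseling randomization (section 4b, Participant Randomization). For counseling, the risk therefore lies in the 6- and 12-month values and enters through the change from baseline.
4. *Do the other safeguards reach it?* Data cleaning is expected to find only extreme cases, and a shift of 0.5 to 1 cm is not extreme. The 4-SD pruning rule is stated for SSB consumption only.
5. *Which measures are free of the problem?* The laboratory values, including the glucose and insulin behind HOMA. Weight is intermediate: a campus instrument, but participant entry.

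**Illustration of size**

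The plan gives no figure for this bias and no SD for waist change, so there is nothing to reproduce. Inputs:

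- Analysable N at 12 months: 550 (section 4c, Aim 1, Power Calculations), so 550/2 = 275 per level of each factor. (80% of 700 is 560; the difference is immaterial here.)
- SD of waist change: assumed, 5 to 8 cm.
- Differential shift b between arms: assumed, 0.5 or 1 cm, with no true effect.
- Alpha 0.05, taken as two-sided; individuals treated as independent.

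SE = SD × √(2/275), which is 0.426 cm at SD 5, 0.512 at SD 6 and 0.682 at SD 8.

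P(significant) = Φ(b/SE − 1.96) + Φ(−b/SE − 1.96).

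| SD (cm) | b = 0 | b = 0.5 cm | b = 1 cm |
|---|---|---|---|
| 5 | 5% | 21.6% | 65.0% |
| 6 | 5% | 16.5% | 49.8% |
| 8 | 5% | 11.3% | 31.1% |

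Example, SD 5 and b = 0.5: b/SE = 0.5/0.426 = 1.17, and Φ(−0.79) + Φ(−3.13) ≈ 0.216.

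Widening the assumed SD to 4 to 10 cm gives 9 to 31% at 0.5 cm and 22 to 83% at 1 cm. Allowing for clustering would enlarge the SE of the ban comparison and lower its percentages.

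**The case against.** The strongest reply is that the plan does not rest on intake and waist alone. It names blood measures beside the anthropometrics and judges each result against a wider pattern. Shared bias in intake and waist would not move the laboratory values, so an attentive analyst might notice. This stands in part: the objectivity claim is sound for blood. But the plan does not require the laboratory values to agree, and the multiple-outcomes paragraph counts anthropometrics as part of the confirming pattern.

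Other points also carry some weight. Remote measurement is a reasonable choice, since the pandemic interrupted anthropometrics in the preceding Sutter trial. The standardized tape and validated instructions may reduce technique error, though they do not prevent arm-dependent reading or entry. The plan's concession concerns survey reports of intake, and a tape reading may be less open to shading.

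A reader might infer that waist is shown to be biased, or is unfit as a primary outcome. The documents support neither: they contain no evidence on the size or presence of such bias. A reader might also set the assumed shifts against the pilot's 2.1 cm waist reduction. That figure is a change over time across both pilot arms, all exposed to a ban. It is not a between-arm effect and cannot serve as the scale.

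**Conclusion.** The point holds as a contradiction within the plan. Section 4c attributes objectivity to a group of measures that includes waist, while sections 1 and 4b make waist self-measured and self-entered by participants who can tell their exposure. Of the two primary outcomes, only HOMA can act as the check that section 4c describes.

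The percentages show that modest differential reporting would be enough to matter at this sample size. They rest on an assumed SD and an assumed shift, ignore clustering, and say nothing about how likely such a shift is. The conclusion does not depend on them. It concerns what the trial may claim from a waist result that stands alone.

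**What to change.** - **Section 4c, Aim 1, Anticipated Problems:** restrict the word objective to the blood measures, and use only these as the check on self-report bias.
- **Same subsection, multiple-outcomes paragraph:** state that agreement between SSB intake and waist, or participant-entered weight, does not count as independent confirmation.
- **Reporting rule:** keep waist as a co-primary outcome but report it as self-measured. State in advance that a waist effect without a consistent 12-month change in HOMA or other laboratory measures will be reported as possibly due to reporting bias, and not as an established adiposity effect.
- **Supporting check:** compare participant-entered weight with the weights already planned for extraction from Epic (section 4b, Medical Record), where available.

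Testing HOMA ahead of waist is not needed; used as a gate, it would cost power for waist. Averaging two self-readings would reduce random error but not a directional shift.

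The cost is wording, one reporting rule and a comparison using data already requested. There are two downsides. A waist-only result will support a weaker conclusion. A 6-month waist result will have no laboratory check, because blood is drawn only at baseline and 12 months.

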Aim 2: Does a multilevel intervention work better? We will assess the effects of combining a brief intervention and SSB sales ban on outcomes. We will compare outcomes for participants exposed to the multilevel intervention ($n=175$) to those who receive the: (a) brief intervention only ($n=175$), (b)

**SUTTER HEALTH
INSTITUTIONAL REVIEW BOARD**

Protocol Summary Form

sales ban only ($n=175$), and (c) no intervention ($n=175$). *We hypothesize that the combined intervention will have a greater effect on outcomes than the brief intervention or sales ban alone. Higher-risk employees (see Aim 1) will benefit more from the multilevel intervention than their lower-risk counterparts.*

Aim 3: (Exploratory): How does the intervention work? We will test whether changes in SSB cravings mediate the effects of the multilevel intervention on outcomes. The multilevel intervention seeks to increase motivation to reduce SSB intake while reducing environmental cues to drink SSBs. *We hypothesize that the multilevel intervention will lead to the greatest reductions in cravings for SSBs, and cravings will mediate its effects on outcomes. We will explore mediation across high-risk groups (see Aim 1).*

2. BACKGROUND:

Obesity and type 2 diabetes are pressing health concerns, particularly for lower-income and ethnic minority employees. Obesity rates are at an all-time high and disparities persist: 49.6% of adult African Americans are currently obese and 44.8% of Latinos, compared to 42.2% of non-Hispanic whites.¹³ Diabetes rates have nearly doubled since 2000.¹⁴ Employers face disproportionately rising obesity-related healthcare costs alongside productivity losses.¹⁵ Obesity is major concern for occupational safety, particularly for physically active nurses, manual workers and technicians at heightened risk for injury.^{15,16}

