We have several primary and secondary outcomes. To avoid bias from multiple statistical tests, we will closely examine patterns of data. Many of the biomarkers are related, for example, as are the anthropometric measurements. Thus, it will be apparent whether or not each result is consistent with the overall pattern of health impacts.

Expected Outcomes: We expect statistically significant main effects for both study condition variables in the ANOVA analysis, specifically that the means for each of the three groups exposed to the sales ban and/or brief interventions will demonstrate more improvement (reduction in HOMA, abdominal adiposity, blood lipids, SSB consumption, BMI, etc.) than those in the group receiving neither intervention. We also anticipate statistically significant coefficients for each study condition variable in the regression analysis that again indicates that those interventions are linked to better outcomes. This would indicate that each intervention has an effect.

Analysis Plan for Aim 2: *Does a multilevel intervention work better?* We will assess the multilevel effects of combining a brief intervention and SSB sales ban on outcomes.

Introduction: The goal of Aim 2 is to test the hypothesis that the combined intervention will have a greater effect on outcomes than the brief intervention or sales ban alone. This is justified by our pilot study findings that employees benefitted most from the multilevel intervention (see Figure 1)¹¹ and by

**SUTTER HEALTH
INSTITUTIONAL REVIEW BOARD**

Protocol Summary Form

the socioecological model which argues that obesity prevention should address multiple levels of intervention at once.⁹⁹

Research Design for Aim 2: The analysis will use ANOVA and regression models similar to those above, but with the key addition of an interaction term for the two interventions, allowing us to explore the possibility that they work better in combination than separately.

Key Measures for Aim 2. Measures are the same as those described above under Aim 1.

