Analytic Plan for Aim 2: Having established the main effects of each intervention under Aim 1, our analyses for Aim 2 focus on the interaction between them. Specifically, we anticipate that the combined intervention will have an effect above and beyond the simple additive effects of the two interventions. This analysis will require replicating the ANOVA and regression models used for Aim 1 with the addition to each of an interaction term for the two interventions. For example, the model predicting HOMA change will include assignment to the sales ban condition (coded as 0/1), assignment to the brief intervention condition (coded as 0/1), the interaction term for the two conditions (sales ban*brief intervention), baseline HOMA, baseline SSB consumption, baseline BMI, race/ethnicity, job classification (if sample size allows, as above), and sex. The procedure for analyzing each outcome is the same, but with each primary and secondary outcome substituted for HOMA in turn. This time, the main variable of interest will be the interaction term. We will graph and deconstruct each significant interaction term to determine the details of the interaction.

Power Calculations: As with Aim 1 above, power calculations are based on findings from the UCSF pilot and retention rates from the Sutter pilot. We will have 175 participants in each of the following groups. With 80% retention, this allows a final N of 550, with approximately 138 in each of the four experimental conditions. Power analysis for a full factorial design conducted with the BDEsize¹⁰⁹ package within R¹¹⁰ indicates that at 80% power and an alpha level of .05 we will be able to detect effect sizes as small as .12 for the interaction between the two interventions.

Anticipated Problems and Alternative Approaches: As with Aim 1, attrition and self-report bias are the primary potential issues we anticipate; handling of each is described above.

Expected Outcomes: We anticipate a significant interaction term, and more specifically, that the effect of the sales ban and brief intervention together will be stronger than each is individually. Participants assigned to the brief intervention and working at sites with a sales ban would thus demonstrate the greatest amount of change, and more change than one would expect if the effect of the two conditions were simply additive.

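### Aim 2 asks whether the combination beats each component alone, but the plan designates and powers only the interaction, which asks a different question

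*Combined protocol and SAP*

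**What the plan says.** Section 1 (Study Aim/Purpose, Aim 2) states the hypothesis that "the combined intervention will have a greater effect on outcomes than the brief intervention or sales ban alone". It also names the comparisons in advance: "We will compare outcomes for participants exposed to the multilevel intervention", set against counselling only, ban only and no intervention, with 175 per group. The Introduction to the Aim 2 analysis plan in section 4c repeats this: "The goal of Aim 2 is to test the hypothesis that the combined intervention will have a greater effect on outcomes".

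The rest of the Aim 2 plan turns to a different quantity. Research Design for Aim 2 adds a product term, "allowing us to explore the possibility that they work better in combination than separately". The Analytic Plan says "our analyses for Aim 2 focus on the interaction between them", explains that "we anticipate that the combined intervention will have an effect above and beyond the simple additive effects of the two interventions", and concludes: "This time, the main variable of interest will be the interaction term". The only follow-up is conditional: "We will graph and deconstruct each significant interaction term to determine the details of the interaction".

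The Aim 2 power statement covers the interaction alone: an effect size of .12 at 80% power and alpha .05, with a final N of 550, about 138 per cell. Expected Outcomes for Aim 2 then merges the two ideas, anticipating both an effect stronger than either component and one that is more than additive.

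**The concern.** Being better than each component and being more than the sum of the components are separate claims. Under additivity the first is true and the second false. A trial that succeeds on the stated hypothesis through additive effects would therefore fail its designated Aim 2 test about 95% of the time, and the deconstruction step would not be triggered.

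Section 4c has no rule for that outcome. A null interaction could be reported as showing that the combination is no better, or as showing that the effects add and so it is better, and the choice would be made after seeing the data. The Aim 1 main effects do not settle it. A main effect equals combined minus the other component only if additivity holds, and a non-significant interaction does not establish additivity.

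A smaller ambiguity affects Aim 1. Section 1 and the Aim 1 Introduction describe each component against neither, whereas the Aim 1 Analytic Plan tests main effects, which average over the other intervention if all four cells are used. The text does not say which answers Aim 1.

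**Working it through.** **Inputs.** From section 4c: N = 550, about 138 per cell, alpha .05, 80% power. From section 1: 16 campuses, 8 per ban condition. Assumed because the documents do not give them: two-sided tests, the metric of the .12, all effect sizes, and the ICC. Effects are in SD units, with positive meaning improvement.

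**Notation.** Cell means are: neither 0, ban a, counselling b, combined a + b + g. Then:
- combined minus ban-only = b + g
- combined minus counselling-only = a + g
- interaction = g
- main effects, averaged over the other factor = a + g/2 and b + g/2

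The stated hypothesis is a + g > 0 and b + g > 0. The designated test is of g. With g = 0 and a, b > 0, the hypothesis is true and the test is at its null.

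**The plan's own figure.** For a 1-df interaction in a balanced 2×2 with N = 550, the detectable Cohen's f is 0.1197, which rounds to .12. Since f = g/4, this is g = 4 × 0.12 = 0.48 SD. So .12 reproduces if it is read as Cohen's f.

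**Detectable differences, no clustering.** The normal approximation is (1.960 + 0.842) × SE:
- two-cell contrast: SE = √(2/138) = 0.120, giving 0.337 (0.338 by noncentral t)
- main effect: SE = √(1/138) = 0.085, giving 0.238 (0.239)
- interaction: SE = √(4/138) = 0.170, giving 0.477 (0.478)

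**How often each test succeeds, by simulation, no clustering.**

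| Assumed truth | Interaction significant | Both contrasts significant | Both main effects significant |
|---|---|---|---|
| a = b = 0.20, g = 0 | 5% | 22% | 42% |
| a = b = 0.30, g = 0 | 5% (2.5% favourable) | 56% | 88% |
| a = b = 0.40, g = 0 | 5% | 85% | 99% |

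**What inferring from main effects can do.** Suppose a reader treats two significant main effects with a null interaction as showing that the combination is better.

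| Assumed truth | Misleading pattern, no clustering | At ICC 0.01, 0.02, 0.05 | Both direct contrasts, no clustering |
|---|---|---|---|
| a = b = 0.40, g = −0.40 (combined equals each component) | 15% | 11%, 9%, 6% | 0.5% |
| a = 0.30, b = 0.50, g = −0.30 (combined equals counselling only) | 24% | 17%, 14%, 9% | 2.1% |

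**Clustering.** Assume a random campus intercept only. Combined minus ban-only is within campus, with variance 2(1 − ICC)/138. Combined minus counselling-only is between campuses, with variance 2[ICC/8 + (1 − ICC)/138], tested on 14 df. At ICC 0.02 the between-campus SE is √(2 × (0.0025 + 0.0071)) = 0.139, and (2.145 + 0.868) × 0.139 = 0.418.

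| ICC | Detectable, combined minus counselling-only | Detectable, combined minus ban-only | Both contrasts at 0.20 | at 0.30 | at 0.40 |
|---|---|---|---|---|---|
| 0.01 | 0.391 | 0.336 | 18% | 47% | 77% |
| 0.02 | 0.418 | 0.334 | 16% | 43% | 73% |
| 0.05 | 0.488 | 0.329 | 12% | 34% | 60% |

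Both main effects at additive 0.30 SD are significant in about 76%, 68% and 49% at these ICCs.

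**The case against.** The interaction may be deliberate. Section 3 describes the interventions as potentially synergistic, and the Analytic Plan expects more than additivity, for which the interaction is the right test. On that reading the fault is loose wording in the hypothesis. This stands in part: the interaction is not a wrong test of synergy. But section 1 and the Aim 2 Introduction both state the weaker hypothesis, and section 1 names its comparisons, so the text needs reconciling either way.

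A favourable interaction does imply superiority over both components if neither component is harmful, since a + g and b + g are then positive. That also stands. The exception needs a harmful component. With a = 0, b = −0.40 and g = 0.40, for example, a favourable interaction appears in 65% of trials and both contrasts succeed in 2.5%, but nothing in the documents suggests harm. The practical gap is the non-significant branch.

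The 15% and 24% rates belong to an inference the plan never states. They require strong antagonism and fall to 6–11% and 9–17% with clustering. They are illustrations only. The main point does not depend on them.

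Finally, the direct contrasts are not powerful. At additive 0.20 SD both succeed in only 22% of trials before clustering. That is a real cost, but it reflects what the design can say about the stated hypothesis.

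**Conclusion.** The concern holds. The designated and powered Aim 2 test does not address the Aim 2 hypothesis as worded, and section 4c supplies no test, alpha, power or decision rule for the named comparisons. When the hypothesis is true through additive effects, the designated test is positive only at the alpha rate (5%, of which 2.5% is in the favourable direction), whatever the size of those effects.

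The logical mismatch needs no assumed numbers. The success rates rest on 138 per cell, two-sided .05, assumed effects, and no clustering unless an ICC is shown. This should be fixed before analysis. The Aim 1 point is a clarification only.

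**What to change.** In the Analytic Plan for Aim 2:

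1. Designate combined minus ban-only (counselling coefficient plus product term) and combined minus counselling-only (ban coefficient plus product term) as the tests of the stated hypothesis. Estimate them from the planned 0/1 model with campus accounted for.
2. Report both whatever the interaction result. Keep the interaction as a separate synergy test.
3. State the decision rule, for example claiming superiority to each component only if both contrasts are significant at .05.
4. State detectable differences: about 0.34 SD per contrast before clustering. With clustering, combined minus counselling-only needs about 0.39, 0.42 and 0.49 SD at assumed ICCs of 0.01, 0.02 and 0.05, while combined minus ban-only stays near 0.33 to 0.34.
5. Report combined minus neither from the same model, since section 1 also names it.

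If more than additivity is the intended hypothesis, reword section 1 and the Aim 2 Introduction to say so.

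For Aim 1, keep the factorial main effects as the primary test and state that they average over the other intervention. Also report the ban-only and counselling-only coefficients against neither, which the Aim 2 model already yields.

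The cost is wording and a new power statement, with the same data and a model already planned. The downside is the power of the both-significant rule. At 0.30 SD it is 56% before clustering, against 88% for inference from main effects, but that inference depends on additivity.
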